## 8.6 Statistical methods

The patient characteristics at randomization, by treatment group, will be presented as mean (SD), median [25th – 75th percentile], minimum, maximum and count (%) depending upon type and distribution. The distribution of baseline characteristics between treatment groups will not be subject to hypothesis testing.

The primary outcome will be measured from the time of randomisation to delivery. Secondary maternal and neonatal outcomes will be measured from the time of recruitment until six weeks after the due date. The significance level for the primary outcome is set at 0.05 and all hypothesis testing will be two-sided. If, and only if, there is a significant difference for the primary outcome, the two secondary outcomes will be tested at a significance level of 0.025. Standard 95% confidence interval (CI) will be used to present the analysis of the primary outcome. The width of the CI used will be adjusted for the secondary outcomes if tested. For raw results data, the primary outcome will be summarized using median [25th – 75th percentile] along with minimum and maximum values.

All secondary outcomes and exploratory outcomes of interest will be presented by number (%) by treatment arm. Primary outcome effect size will be presented as difference in medians and 95% CI, adjusted for gestational age strata based upon the quantile regression model. P-values will be reported with associated with 95% CI for the secondary outcomes if tested. Exploratory outcomes will be presented with 95% CI.

Modelling will use quantile regression to assess difference in median prolongation between groups. This will be supplemented by survival analysis (i.e. time until delivery), using Cox proportional hazards regression (CPH) and Kaplan-Meier survivorship curves. Survival outcomes will not be subject to hypothesis testing. For both quantile regression and survival analysis effect estimates will be presented as group difference with 95% CI.

The number of events for each of the composite binary outcomes is likely to be small. An exact logistic regression model containing treatment group and gestational age strata will be used. In the event that it is not possible to obtain estimates, due to small counts each hypothesis will be tested, unadjusted for gestational strata, using Fisher's exact test. Point estimates of percentage and exact 95%CI will also be provided.

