Given the sample size of 65 per arm this study has a power of 0.9 to detect a difference of 9 days which translates to an ability to detect only a Hazard Ratio ~ 0.5 or smaller.

All secondary outcomes are binary with expected incidence less than 0.05. At the projected sample size of 65 the power to detect a 50% change in incidence is low at 0.12.

12. Framework

This trial uses a superiority hypothesis testing framework between treatment groups for all outcomes.

13. Statistical Interim analyses and stopping guidance

This is a phase II trial with mothers under direct in hospital observation which facilitates immediate detection and management of adverse events. For the planned sample size only a very large treatment effect size would lead to an indication to cease the trial for efficacy at information fraction of 60 – 80%. Given the phase II nature of the study, the complete observation of mothers whilst under trial treatments, there is no planned interim analysis for efficacy. There is no planned interim assessment for futility. The DMC will monitor for adverse events and will provide stopping guidance should this be deemed necessary. See separate DMC charter (PI2 DMSC Charter version 16 June 2018).

14. Timing of final analysis

Unblinding and final analysis will be performed only after all participants have being delivered and all neonatal follow-up has been completed. Neonatal death is one of the outcomes within the prespecified composite neonatal outcome (see protocol p 38 – 39) and is assessed at six weeks post-delivery. Therefore, analysis is will not commence prior to six weeks after the delivery of the last recruited trial patient. Publication of biomarker results may be published separately from the clinical trial outcomes.

15. Timing of outcome assessments.

The primary outcome is measured from time of randomization to delivery. Secondary maternal and neonatal composite outcomes are measured from time of recruitment until six weeks after the due date, with timing dependent upon outcome measures.

Section D: Statistical Principles

16. Confidence intervals and p-value

The significance level is set at 0.05 and all hypothesis testing will be two-sided. A single primary outcome is tested at a significance level of 0.05. If and only if a significant difference is found will the secondary outcomes be tested. The two secondary outcomes will each be tested at a significance level of 0.025.

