17. Description of any planned adjustment for multiplicity, and if so, including how the type 1 error is to be controlled

No adjustment for multiplicity will be performed. The strategy for outcome testing is pre-specified and maintains the overall trial error rate at 0.05.

18. Confidence intervals (CI) to be reported

Standard 95% confidence intervals will be used to present analysis of the primary adjusted outcome. For secondary outcomes it is planned to the adjusted width of CI used.³

19. Adherence and Protocol Deviations

Adherence:

Trial medication will be administered to mothers on an inpatient basis. Measures to monitor adherence are: The trial medication will be written up on the treatment chart and the chart will be signed by the nursing staff to confirm that the participant has taken the medication and to confirm compliance. The research midwife will monitor the treatment chart to assure compliance. The dosing schedule details a programmed escalation of dose in the of side effects. We will use two measures of dosing in the metformin arm: (i) average daily dose of tablets = number of ingested medications/days of therapy and (ii) percentage of maximum dose = ingested medications/ total maximum medications.

Description of how adherence to the intervention will be presented:

Adherence will be presented on the two measures detailed above, using descriptive statistics (N, mean, SD, median, minimum, maximum) converted to metformin dose for the intervention arm.

Definition of protocol deviation for the trial and description in trial results:

Protocol deviations due to errors in applying inclusion/exclusion criteria, the wrong intervention being administered will be documented in trial results either in patient flow diagram or text. The primary outcome will not be subject to ascertainment error due to its unambiguous nature. Prior to unblinding of treatment all protocol deviations will be assessed, and determination made about inclusion of these participants within the trial analysis populations. Determinations will be presented in the research results in the patient flow diagram and possibly in the text.

³ Ludbrook J. Multiple inferences using confidence intervals. Clin Exp Pharmacol Physiol 2000;27:212 - 215.

19. Analysis populations.

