Composite secondary outcome definitions:

(i) Maternal composite outcome: the occurrence of any of the following serious maternal outcomes: maternal death, eclampsia, pulmonary oedema (oxygen saturation $\leq 90\%$, with clinical symptoms requiring treatment), severe renal impairment or the need for dialysis, a cerebral vascular event, placental abruption and liver haematoma or rupture.

(ii) Neonatal composite outcome: the occurrence of any of the following serious neonatal outcomes: neonatal death within 6 weeks after the expected due date, grade III or IV intraventricular haemorrhage, necrotizing enterocolitis and bronchopulmonary dysplasia

Exploratory outcomes:

All other outcomes, including outcomes nested within individual secondary outcomes or outcomes with less clinical interest than secondary outcomes are classified as exploratory outcomes. These will not be subject to hypothesis testing, but precision of point estimates and may be presented using unadjusted 95%CI.

24. Statistical Analysis methods

Raw data primary outcome:

For raw results data, the primary outcome will be summarized using median [25th – 75th percentile] along with minimum and maximum values. All secondary outcomes and exploratory outcomes of interest will be presented by number (%) by treatment arm. Primary outcome effect size will be presented as difference in medians and 95%CI, adjusted for gestational age strata based upon the quantile regression model p-values will be reported associated with 95%CI for all testable outcomes.

Primary outcome:

Modelling will use quantile regression to assess difference in median prolongation between groups. This will be supplemented by survival analysis (i.e. time until delivery), using Cox proportional hazards regression (CPH) and Kaplan-Meier survivorship curves. Survival outcomes will not be subject to hypothesis testing. For both quantile regression and survival analysis effect estimates will be presented as group difference with 95% confidence intervals (95%CI).

Secondary outcomes:

The number of events for each of the composite binary outcomes is likely to be small. An exact logistic regression model containing treatment group and gestational age strata will be used. In the event that it is not possible to obtain estimates, due to small counts each hypothesis will be tested, unadjusted for gestational strata, using Fisher's exact test. Point estimates of percentage and exact 95%CI will also be provided.

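### Optional improvement: a Holm step-down could replace the fixed 0.025/0.025 split for the two gated composites at the same 0.05 error rate; at the SAP's own event rates the gain is negligible

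*SAP*

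**What the plan says.** The two documents agree on the testing order. SAP item 16 sets the overall level ("The significance level is set at 0.05 and all hypothesis testing will be two-sided") and the gate ("If and only if a significant difference is found will the secondary outcomes be tested"). It then fixes the level behind the gate: "The two secondary outcomes will each be tested at a significance level of 0.025". Protocol 8.6 has the same rule: "the two secondary outcomes will be tested at a significance level of 0.025". SAP item 17 states what this achieves: "The strategy for outcome testing is pre-specified and maintains the overall trial error rate at 0.05". Neither document passes the level of a rejected composite on to the other.

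The secondary outcomes are the maternal and neonatal composites. SAP item 24 names the test: "An exact logistic regression model containing treatment group and gestational age strata will be used". Unadjusted Fisher's exact test is the fallback. SAP item 18 and protocol 8.6 plan confidence intervals of adjusted width for the secondaries. Protocol 8.6 then also refers to 95% intervals alongside their p-values.

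SAP item 11 gives the expected rates and power: "All secondary outcomes are binary with expected incidence less than 0.05" and "At the projected sample size of 65 the power to detect a 50% change in incidence is low at 0.12". Protocol 14.2 adds that the trial is not powered for maternal or neonatal outcomes.

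**The concern.** A significant primary result releases the full 0.05 to the two composites. Under the fixed split, once one composite is rejected its 0.025 is spent and the other is still held to 0.025. Holm lets the second composite be tested at 0.05 at that point, with no increase in the family-wise error rate. So there is one pattern of results, one composite with p at or below 0.025 and the other with p between 0.025 and 0.05, in which the plan declares one finding where the same error budget would allow two. At stake is a second secondary claim in a trial that has already succeeded on its primary outcome and on one composite.

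**Working it through.** **Inputs.** From the documents: overall two-sided 0.05 with a gate on the primary, and 0.025 per composite (SAP 16, protocol 8.6); expected incidence below 0.05, with a 50% change considered (SAP 11); 65 per arm at analysis and 75 per arm randomised (SAP 11); exact tests (SAP 24). Assumptions: the composites are independent, unstratified Fisher stands in for stratified exact logistic regression, and any control rate above 5% is hypothetical.

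**1. The plan's own power figure.** For 5% vs 2.5% at 65 per arm, the normal approximation at two-sided 0.05 gives 0.113, close to the stated 0.12. At the 0.025 level actually planned it gives 0.068. The stated figure therefore matches a test at 0.05.

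**2. Error rate.** The fixed split spends 0.025 + 0.025 = 0.05. For Holm:
- Both composite nulls true: a false rejection needs the smaller p ≤ 0.025, with probability at most 0.025 + 0.025 = 0.05.
- One null true: rejecting it needs its p ≤ 0.05, with probability at most 0.05.
- Primary null true: nothing behind the gate is tested unless the primary is falsely rejected, with probability at most 0.05.

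These bounds hold under any correlation between the composites.

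**3. Power formulas.** Let a1, a2 be the maternal power at 0.025 and 0.05, and b1, b2 the neonatal power. With independence:
- Maternal power: a1 (fixed split); a1 + (a2 − a1)·b1 (Holm).
- Both significant: a1·b1 (fixed split); a1·b2 + a2·b1 − a1·b1 (Holm).
- At least one: 1 − (1 − a1)(1 − b1) under both rules, because the first rejection always needs p ≤ 0.025.

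**4. At the SAP's rates** (both composites 5% vs 2.5%; all 2×2 tables enumerated, Fisher):
- 65 per arm: a1 = b1 = 0.0101, a2 = b2 = 0.0261. Holm power per composite = 0.0101 + 0.0160 × 0.0101 ≈ 0.0102. Both significant: 0.0001 → 0.0004. At least one: 0.020 either way.
- 75 per arm: a1 = b1 = 0.0161, a2 = b2 = 0.0371. Holm power per composite = 0.0161 + 0.0210 × 0.0161 ≈ 0.0165. At least one: 0.032 either way.

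Without independence, the gain per composite cannot exceed the smaller of P(other p ≤ 0.025) and P(0.025 < own p ≤ 0.05). At 65 per arm that is the smaller of 0.0101 and 0.0160, or about 1.0 percentage point.

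**5. At higher, assumed rates** (75 per arm, neonatal 40% vs 20%, so b1 = 0.615 and b2 = 0.714):

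| Maternal rates | a1, a2 | Maternal power, fixed → Holm | Both significant, fixed → Holm | At least one (both rules) |
|---|---|---|---|---|
| 10% vs 5% | 0.073, 0.128 | 7.3% → 10.7% | 4.5% → 8.6% | 64.3% |
| 15% vs 5% | 0.318, 0.445 | 31.8% → 39.6% | 19.5% → 30.5% | 73.7% |

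First row, maternal: 0.073 + (0.128 − 0.073) × 0.615 ≈ 0.107. The second row assumes a two-thirds reduction, larger than the SAP's 50%. With 15% halved to 7.5%, maternal power goes from 14.3% to 19.6%.

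**6. Conditioning.** All these figures assume that the gate has been passed. With the planned 90% power on the primary, and independence from it, each is multiplied by 0.9.

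**7. Exact-test conservatism, separately.** At a true 5% rate in both arms and 65 per arm, Fisher's actual size at nominal 0.025 is 0.0044. For 5% vs 2.5%, power at 0.025 drops from 0.068 (normal approximation) to 0.010 (Fisher). That loss is far larger than the loss from the split, and Holm does not restore it.

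**The case against.** The strongest reply is that nothing here is wrong. A prespecified Bonferroni split behind a gate is standard, the two documents agree, and the 0.05 claim in SAP 17 is correct. The sponsor already discloses low power for the secondaries, and at the stated incidence Holm changes almost nothing. The fixed split also pairs exactly with 97.5% intervals, so test and interval always agree; Holm breaks that match. All of this stands, and it is why the change is optional.

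Three stronger readings are tempting and are not supported:
- **That the split is a mistake or costs the planned trial material power.** The sizeable gains need control rates of 10% to 40%, which appear nowhere in the documents. The SAP expects less than 5%.
- **That Holm raises the chance of a secondary finding.** It does not. It helps only the second composite, after the first has been rejected.
- **That Holm cures the conservatism of the exact tests.** It does not. A mid-P version would recover some power but gives up guaranteed size (up to 0.027 found at nominal 0.025). It is a different trade-off and is not recommended here.

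On the other side, the under-5% figure is a single unsourced sentence covering all secondary outcomes. If either composite proves commoner, Holm protects power at no cost in error rate. The pairing with intervals is also not yet settled, because protocol 8.6 mentions both adjusted-width and 95% intervals.

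**Conclusion.** The point holds as a cheap, optional efficiency improvement. For testing, Holm is never worse than the fixed split and keeps the family-wise error at 0.05; this needs no assumption about event rates or correlation. Its size does depend on them. The gain is about 0.01 to 0.03 percentage points per composite at the SAP's rates. It is about 3 points of maternal power at an assumed 10% vs 5%, and about 8 points at an assumed 15% vs 5%, each with an assumed neonatal 40% vs 20% at 75 per arm. These sizes rest on Fisher as a stand-in for the stratified exact test, independent composites and a significant primary result. A sponsor that keeps the fixed split has a valid plan.

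**What to change.** In SAP 16 and protocol 8.6, replace the fixed-level sentence with: *If the primary outcome is significant, the two composites are tested by the Holm procedure: the smaller p-value against 0.025 and, if significant, the larger against 0.05.*

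In SAP 18 and protocol 8.6, state that 97.5% confidence intervals are reported for both composites, and that a composite rejected at the second step may have a 97.5% interval that includes no effect. Remove the competing reference to 95% intervals for the tested secondaries in protocol 8.6. SAP 17 could be tidied at the same time, since it says that no multiplicity adjustment is made although 0.025 each is one.

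The cost is a few sentences across the two documents, with no change to sample size, data collection or the tests themselves. The real price is that test and interval can disagree for a second-step rejection. The change should be made before unblinding.

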### **7.3 Expectant management for pre-eclampsia**

#### **7.3.1 Routine management**

Expectant management for early onset pre-eclampsia involves admission to hospital until delivery with close maternal and fetal surveillance.

Maternal surveillance includes four hourly blood pressure measurement, twice daily clinical assessment, daily urinalysis, and twice weekly assessments with blood tests (full blood count, renal function tests and hepatocellular enzymes if HELLP syndrome is suspected) and 24-hour urinary protein measurement on admission.

Fetal surveillance includes six-hourly cardiotocography and ultrasound assessments every two weeks (or more frequently if clinically indicated) for Doppler velocimetry of the umbilical artery, middle cerebral artery, ductus venosus, amniotic fluid volume assessment and growth.

All participants will receive two doses of betamethasone 24 hours apart to reduce the risks of neonatal respiratory distress syndrome, intracranial haemorrhage and necrotising enterocolitis. A single repeat dose is usually given one week later as per hospital protocol.

Most participants will be on antihypertensive treatment and the medication used will be documented. All women should already be receiving iron and folic acid supplementation.

Clinical care will be left up to the discretion of the clinical team. The indication for delivery will be a clinical decision. Indications for delivery may include failure to control blood pressure, the development of major maternal or fetal complications. Expectant management will usually end at a gestation of 34 weeks with planned delivery.

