Sample size calculation is determined by the primary research question: does treatment with metformin result in a gain in the length of gestation of greater than or equal to 5 days compared to the mother receiving placebo therapy. For each mother her gestational age at diagnosis (trial enrolment) sets the maximum allowable length of pregnancy prolongation. For those with PE diagnosed at 31+6 will be delivered at 34 weeks (should they reach that gestation, as it is unit policy to deliver at that gestation) thus setting a ceiling for maximal prolongation of 15 days. Therefore, the maximum potential gestation prolongation is 63 days for stratum 1 and 42 days for stratum 2 mothers. The primary outcome will be the median prolongation of gestation, reflecting the skewed distribution of the gestation prolongation seen in published clinical trials.¹ The researchers believe that median prolongation a more clinically meaningful measure of change than either raw mean or ratio change. Sample size calculations were based upon the Geometric Mean Ratio (GMR), an appropriate measure for differences in median. Analysis was performed both using PASS 13 (Power Analysis and Sample Size Software (2014). NCSS, LLC. Kaysville, Utah, USA, ncss.com/software/pass) and the Powercal program running in Stata v15 (Stata statistical software. 2017 Release 15. Stata Corp. College Station, TX: StataCorp LLC).

Power calculations settings were: 90% power, with two-sided alpha set at 0.05, median prolongation of 8.3 days in the control arm and a clinically important gestation prolongation of 5 days. The measure of variability used in this analysis is the coefficient of variation (CV) in mothers treated with standard expectant

¹ Hall DR, Odendaal HJ, Kirsten GF, et al. Expectant management of early onset, severe pre-eclampsia:

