Adjustment for covariates for each primary and secondary outcomes:

Primary outcome: A covariate adjusted analysis with both treatment group and gestational age design-based strata modelled as fixed will constitute the primary analysis outcome. Unadjusted and adjusted CPH analysis are only supplemental to this primary analysis.

Secondary outcomes: Composite binary outcomes will be modelled using a logistic regression model containing both treatment group and gestation aged based strata.

Methods used for assumptions to be checked for statistical methods:

Quantile regression makes no distributional assumptions (assessed using residuals) apart from assuming the outcome is continuous. Secondary outcomes tested using exact logistic regression or Fisher's exact test make no distributional assumptions.

Sensitivity analyses:

Sensitivity analysis will be conducted on the primary outcome are:

- (i) Treatment received Analysis will be adjusted by median quantile regression as already specified for the primary outcome intention to treat analysis. Treatment received, given varying dosage schedule is defined as an average daily dose.
- (ii) Gestational age as an effect modifier. An interaction between treatment and gestational age strata will be using the same model as the primary outcome. Given study size it is acknowledged that this has low power to detect an interaction effect.
- (iii) Covariate adjusted. The trial investigators consider that a mother with absent UAD flow, an estimated fetal weight less than the 10th centile and an estimated fetal weight less than the 3rd centile are more likely to

be associated with shorter randomization to delivery times. Covariate adjustment for these factors may increase the precision of the primary outcome measure if there is a correlation between them and delivery time.

(iv) Survival analysis. Will be performed using Cox proportional hazards regression (CPH) adjusted for gestational age strata and Kaplan-Meier survivorship curves.

No sensitivity analysis for primary outcome outcomes is planned for missing data as we expect these mothers not to have missing outcome data or baseline measured pretreatment covariates. If the neonate is lost to follow-up the outcome will be set to missing, a sensitivity analysis will be performed to assess strength of inference given pattern of missingness by setting missing values to no event, mean event rate or event to assess dependence on inference on the unknown outcomes.

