Subgroup analyses

Gestational age at randomization has been incorporated in the prespecified primary outcome analysis. No other subgroup analyses are planned.

25. Missing data reporting and assumptions/statistical methods to handle missing data

In this study primary outcome will not have missing data, both gestational age at randomization and treatment are predetermined and all mothers will deliver in the acute in hospital setting. Based upon our experience in the PIE 1 trial (at the same institution) we expect no of missing covariate values for the three components required for analysis of the POM – group assignment, gestational age-based strata and time to delivery (delivery time – admission time). Imputation will not be performed. As described above, if an FDIU occurs it will be allocated a time of zero prolongation.

Secondary outcomes that are pre-specified for hypothesis testing use the same pre-randomization covariates and all outcomes are identifiable. If neonate is lost to follow-up the outcome will be set to missing, a sensitivity analysis will be performed to assess strength of inference given pattern of missingness by setting missing values to no event, mean event rate or event to assess dependence on inference on the unknown outcomes.

26. Additional Analyses

For the primary outcome a prespecified analysis assessing effect of absent uterine artery flow on outcome will be performed by a covariate adjusted analysis that includes treatment group, the gestational age design-based strata, fetal growth restriction (defined as an estimated fetal weight less than the 10th centile and less than the 3rd centile and absent flow on umbilical artery Doppler (UAD) examination measured at the time of randomization. The trial investigators consider that a mother with fetal growth restriction or absent UAD flow was more likely to be associated with shorter randomization to delivery times. This pre-specified covariate adjustment will increase the precision of the primary outcome measure if there is a correlation.

27. Harms

The number (and percentage) of patients experiencing serious adverse events (SAE) will be presented for each treatment arm. These are: maternal death, fetal death, event resulting threat to life of mother or baby, event that causes prolonged hospital stay, event resulting in significant disability to mother and congenital birth defect not previously detected on ultrasound. All will be listed by trial arm in

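### The supplemental Cox model counts planned 34-week deliveries as events; a second analysis censored at 34+0 would show the effect before that limit

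*SAP*

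**What the plan says.** SAP section 24 makes quantile regression of the median the primary analysis and adds: "This will be supplemented by survival analysis (i.e. time until delivery), using Cox proportional hazards regression (CPH) and Kaplan-Meier survivorship curves". Sensitivity analysis (iv) in the same section repeats it: "Will be performed using Cox proportional hazards regression (CPH) adjusted for gestational age strata and Kaplan-Meier survivorship curves". Protocol 8.6 carries the same plan. Both documents call the Cox analysis supplemental and exclude survival outcomes from hypothesis testing.

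Neither document gives a censoring rule or separates planned from indicated delivery. SAP section 25 expects that "all mothers will deliver in the acute in hospital setting". Read together, these mean that every delivery is an event, although the SAP does not say so in words.

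Both documents also describe an end point set by policy. Protocol 7.3.1 says "Expectant management will usually end at a gestation of 34 weeks with planned delivery". SAP section 11 gives the consequence for a woman enrolled at 31+6 ("should they reach that gestation, as it is unit policy to deliver at that gestation"), "thus setting a ceiling for maximal prolongation of 15 days". The next sentence of the SAP states that "the maximum potential gestation prolongation is 63 days for stratum 1 and 42 days for stratum 2 mothers". The ceiling is not mentioned again in the survival analysis.

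**The concern.** A woman still pregnant at 34 weeks has gained all the time that the policy allows, yet in the Cox model she fails on that day. The day is fixed by her gestational age at entry, and the same rule applies in both arms, so her delivery says almost nothing about treatment. If metformin works, more metformin women reach that day, and more of that arm's events are of this uninformative kind. The hazard ratio then mixes two things: how far the drug delays delivery before the limit, and a calendar rule common to both arms. The Cox model adjusts for two gestational-age strata only, while the ceiling varies by 20 days within each.

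At stake is how a supporting estimate is read. The hazard ratio and its 95% interval will be presented as a supplement to the primary result, and nothing in the plan tells the reader how much of it reflects planned delivery.

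**Working it through.** **Inputs.** From SAP section 11: medians of 9 and 14 days (survival table), medians of 8.32 and 13.32 days with CV 1.0 (main sample size), 65 women per arm, and delivery at 34 weeks. From SAP section 10: strata 26+0 to 28+6 and 29+0 to 31+6. Assumed, because the documents do not give them: entry age uniform within stratum, strata of equal size, every woman still pregnant delivered at 34+0, and the shape of the time distribution.

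**The SAP's own figures.** For 9 against 14 days, HR = 9/14 = 0.643, which matches the stated 0.64. The group sizes do not follow if every woman has an event. The Schoenfeld formula gives events = 4(1.960 + 1.282)² / (ln HR)². For 0.643 that is 42.03/0.195 = 215 events, or 108 per group against the stated 158. For 0.50 it is 42.03/0.480 = 87.5 events, or 44 per group against 68. The column reappears if about 24% of controls have no event. For example, 0.24^0.643 = 0.400 in the treated arm, and 215 / [1 − (0.24 + 0.400)/2] / 2 = 158. The documents do not state that input. It shows only that the event definition is not written down.

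**Ceilings.** 34+0 is day 238. Entry at 26+0, 28+6, 29+0 and 31+6 is day 182, 202, 203 and 223, so the ceilings are 56, 36, 35 and 15 days. The SAP's 63 and 42 days fit day 245 (35+0): 245 − 182 = 63 and 245 − 203 = 42. They do not fit 34+0 or the SAP's own 15 days.

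**Share reaching 34+0.** With exponential times of median m, the share is the mean of 2^(−c/m) over ceilings c = 15 to 56. For m = 9 it is 9.7%; for m = 14 it is 20.5%.

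**Cox model with treatment and stratum,** 400,000 simulated women per row:

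| Scenario | Reach limit, placebo / metformin | HR, all deliveries | HR, censored at limit | HR, no limit |
|---|---|---|---|---|
| Exponential, 9 / 14 | 9.7% / 20.5% | 0.682 | 0.642 | 0.642 |
| Exponential, 8.32 / 13.32 | 8.3% / 19.1% | 0.663 | 0.625 | 0.626 |
| Same, limit at 35+0 (63 and 42 days) | 4.6% / 13.3% | 0.646 | 0.624 | 0.623 |
| Log-normal, CV 1.0, 8.32 / 13.32 | 6.7% / 15.9% | 0.616 | 0.583 | 0.600 |
| Log-normal, CV 0.8, 8.32 / 13.32 | 4.3% / 12.7% | 0.554 | 0.530 | 0.542 |
| Exponential, 9 / 18 | 9.7% / 28.4% | 0.561 | 0.499 | 0.500 |

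Repeat runs of the first row gave 0.68 to 0.69 against 0.64 to 0.65. Its log shift is ln(0.682/0.642) = 0.060, or 14% of |ln 0.642| = 0.443. In the last row, where the gain is 9 days and not the planned 5, the shift is ln(0.561/0.499) = 0.117.

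**Against precision.** In 3,000 simulated trials of 130 women (exponential, 8.32 / 13.32), the mean HR was 0.654 with all deliveries and 0.621 with censoring, a log shift of 0.052. The standard errors were 0.181 and 0.194. So 0.052/0.194 = 0.27, and the first row's shift gives 0.060/0.181 = 0.33.

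**Primary analysis.** With the limit applied, the simulated medians stay at 9.0 and 14.0 days (first row) and 8.4 and 13.3 days (second row), because both planned medians lie below the lowest ceiling of 15 days. Only in the 9 / 18 row is a median affected (16.8 instead of 18 days).

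**The case against.** The strongest reply is that the trial's outcome is time to delivery, whatever the reason. A planned delivery at 34 weeks is a delivery, and for that outcome counting it is right. The Cox analysis is also supplemental and untested. All of this stands, so the plan contains no error here.

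Censoring is not a route to a single true value either. In the log-normal sample-size model hazards are not proportional, and the censored ratio (0.583) lies about as far from the no-limit ratio (0.600) as the all-deliveries ratio does (0.616). The limit is also soft: the protocol says planned delivery usually comes at 34 weeks, and some women are entered on fetal weight because their dates are uncertain.

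A reader might infer four stronger things that the documents do not support.

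- That the hazard ratio understates the primary effect. The primary effect is a difference in median time to any delivery, a different quantity.
- That the strata will falsely appear to differ. In the 9 / 14 example the gap is indeed mostly in stratum 2 (0.712 against 0.646, compared with 0.654 against 0.639 in stratum 1). But no stratum-specific hazard ratio is planned, and the only treatment-by-stratum interaction uses the median model.
- That the Kaplan-Meier curves are biased. They remain a valid description of time to delivery, with drops at the ceilings.
- That power is lost. No survival test exists to lose it.

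What survives is narrower: one hazard ratio answers one question, and the plan does not say which.

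**Conclusion.** The point holds as a modest, inexpensive improvement. The planned Cox analysis validly describes delivery from any cause. Relative to the hazard ratio for delivery before the policy limit, it is pulled towards 1 if metformin works: about 0.68 to 0.69 instead of 0.64 to 0.65 in the SAP's 9 against 14 day example, a log shift of about 0.05 to 0.07. With 130 women that is roughly a quarter to a third of one standard error. The direction was the same in every scenario tried. The size rests on the assumed time distribution, entry ages, strata split and strict delivery at 34+0; it is smaller if the limit falls later and larger if the drug effect is larger. At the planned effect, the primary median regression is essentially unchanged.

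**What to change.** In SAP section 24 (primary outcome and sensitivity analysis iv) and protocol 8.6:

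- Keep the Cox analysis of all deliveries, and say that planned 34-week deliveries count as events in it.
- Prespecify beside it a Cox analysis in which the event is delivery before 34+0 and women still pregnant at 34+0 are censored then.
- Report the number reaching 34+0 by arm and stratum.
- State that for women with uncertain dates the 34+0 date rests on the gestational age estimate made at randomisation.
- In SAP section 11, reconcile the 63- and 42-day maxima with delivery at 34 weeks and with the 15-day figure.

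The primary analysis and the Kaplan-Meier curves stay as they are. The cost is a few sentences and one more model, using gestational age at randomisation, which is already recorded. The drawback is small: the censored hazard ratio refers only to delivery before 34 weeks, and about 7 to 21% of women, depending on arm and model, contribute no event to it under the planned effect.
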